3.7.5 Treatment Interruption and Discontinuation

In this trial, it is expected that subjects may possibly have one or more planned or unplanned treatment interruptions. If a subject's IMP treatment must be interrupted for medical or surgical reasons, liver test abnormalities, use of a prohibited medication, or other reasons (eg, hospital admission for an invasive procedure, a major medical condition, surgery, dental work, or a temporary situation that prevents subject compliance with the IMP administration schedule), the investigator should be notified as soon as possible and the reason for treatment interruption must be documented in the source documents and case report form (CRF). If permissible, the subject's IMP may be resumed following approval by the medical monitor.

If IMP treatment is permanently discontinued, the reason for discontinuation must be recorded appropriately in the source document and in the CRF.

A subject who permanently discontinues IMP treatment ends trial participation and the early termination visit should be completed.

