3.8.3 Individual Subject

If a subject discontinues the trial prematurely, the reason must be fully evaluated and recorded appropriately in source documents and the CRF. If the subject is being withdrawn because of an AE, that AE should be indicated as the reason for withdrawal.

All subjects have the right to withdraw at any time during treatment without prejudice. The investigator can discontinue a subject's participation in the trial at any time if medically necessary. It is preferred that subjects who permanently discontinue IMP will have the option to continue participation off IMP with regular scheduled visits or with a modified (ie, less frequent) schedule. If subjects are unable or unwilling to complete the visits and procedures off IMP, the early termination/EoTx visit should be completed. The investigator may continue to contact those who discontinue IMP through to the final completion date of the trial or thereafter if needed to determine outcomes ie, vital status.

In addition, subjects meeting the following criteria must be withdrawn from the trial:

- a) Occurrence of any AE, intercurrent illness, or abnormality in a laboratory assessment which, in the opinion of the investigator, warrants the subject's permanent withdrawal from the trial;
- b) Subject noncompliance, defined as refusal or inability to adhere to the trial schedule or procedures (see [Section 3.12](#));
- c) At the request of the subject, investigator, sponsor, or regulatory authority;
- d) Subject is lost to follow-up.

Protocol 156-13-211

The investigator will notify the sponsor promptly when a subject is withdrawn.

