3.12 Subject Compliance

Subject compliance will be monitored by pill counts as IMP is returned. Any subject who, without the instruction of the investigator, discontinues tolvaptan investigational product, discontinues tolvaptan for 30 consecutive days or misses > 30% of the doses intended for a period between visits (whichever is greater) will be deemed noncompliant. Depending on the circumstances leading to noncompliance, the subject may be withdrawn from the trial or discontinued from investigational product administration by the investigator and/or sponsor. It is preferred that subjects who discontinue tolvaptan, or are withdrawn by the investigator for reasons other than noncompliance or lost to follow-up, will continue with regularly scheduled visits completing all procedures as provided in the protocol.

Protocol 156-13-211

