5.5 Follow-up of Adverse Events

For this trial, AEs will be followed up for 7 days after the last dose of tolvaptan has been administered (follow-up period).

Subjects experiencing SAEs should be followed clinically until their health has returned to baseline status, or until all parameters have returned to normal, or have otherwise been explained.

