5.5.1 Follow-up of Nonserious Adverse Events

Nonserious AEs that are identified on the last scheduled contact must be recorded on the AE eCRF with the current status noted. All nonserious events that are ongoing at this time will be recorded as ongoing on the eCRF.

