5.5.2 Follow-up of Post-Trial Serious Adverse Events

Serious AEs that are **identified on the last scheduled contact** must be recorded on the AE eCRF page and reported to the sponsor according to the reporting procedures outlined in [Section 5.3](#). This may include **unresolved previously reported** SAEs, or **new SAEs**. The investigator will follow SAEs until the events are resolved, or the subject is lost to follow-up. Resolution means the subject has returned to the baseline state of health, or the investigator does not expect any further improvement or worsening of the subject's condition. The investigator will continue to report any significant follow-up information to OPDC up to the point the event has been resolved.

Protocol 156-13-211

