Section 5.3, Immediately Reportable Events	The investigator must immediately report within 24 hours after either the investigator or site personnel become aware of any SAE, an AE that necessitates IMP discontinuation, any new liver result meeting the AE laboratory threshold criteria, any AE of special interest or a confirmed pregnancy , by telephone or by fax to the sponsor as outlined in Appendix 1. An IRE form must be completed and sent by fax, email or overnight courier to the sponsor. (Please note that the IRE form is NOT the AE eCRF).	The investigator must immediately report within 24 hours after either the investigator or site personnel become aware of any SAE, new liver laboratory abnormality requiring special liver eCRF completion, or confirmed pregnancy , by telephone or by fax to the sponsor as outlined in Appendix 1. An IRE form must be completed and sent by fax, email, or overnight courier to the sponsor. (Please note that the IRE form is NOT the AE eCRF).
Appendix 5, Title change	Protocol Amendment	Protocol Amendments and Administrative Changes

ADDITIONAL RISK TO THE SUBJECT:

There is no additional risk to the subjects.

Protocol 156-13-211

Amendment Number: 2**Issue Date:** 06 Mar 2015**PURPOSE:**

The purpose of this amendment was to increase the window from 30 days to up to 3 months to allow use of historical laboratory values for screening, to add flexibility and allow combining of screening and baseline visits in the trial, and to provide clarification on trial discontinuation. The list of vendors was updated. Minor linguistic changes were made for clarity and typographical errors were corrected.

BACKGROUND:

Eligible subjects enrolling from Trials 156-08-271 or 156-13-210 can enroll before they complete the last visit in their respective trials, and the last visit as well as the screening and baseline visit in this trial can be combined into one visit with all required assessments from each visit performed only once, so long as the time between the last visit assessments from the previous trial and the screening visit for this trial is within 30 days.

Other Revisions

Figure 3.1-1 - Trial Design Schematic

Table 3.4.2-1 - Inclusion Criteria

Table 3.4.3-1 - Exclusion Criteria

Table 3.7-1 - Schedule of Assessments footnotes

Sectional Revisions

Location	Old Text	Updated Text

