Protocol 156-13-211

List of Abbreviations and Definition of Terms

Abbreviation	Definition
AE	Adverse event
ALP	Alkaline phosphatase
ALT	Alanine aminotransferase
AST	Aspartate aminotransferase
BUN	Blood urea nitrogen
CRF	Case report form
CRO	Clinical Research Organization
ECG	Electrocardiogram
EDC	Electronic data capture
EU	European Union
EudraCT	European Clinical Trial Data Base
FDA	(United States) Food and Drug Administration
GCP	Good Clinical Practice
ICF	Informed consent form
ICH	International Conference on Harmonisation
IMP	Investigational medicinal product
IND	Investigative new drug
IRB	Institutional review board
IRE	Immediately reportable event
MedDRA	Medical Dictionary for Regulatory Activities
PE	Physical examination
SAE	Serious adverse event
TEAE	Treatment-emergent adverse event
US or USA	United States or United States of America
ULN	Upper limit of normal

Protocol 156-13-211

1 Introduction

This Statistical Analysis Plan (SAP) documents the statistical methodology and data analysis algorithms and conventions to be applied for statistical analysis and reporting of efficacy and safety data of study 156-13-211. The original protocol (dated 20 May 2014), the Amendment 1 (dated 14 July 2014), and the Amendment 2 (dated 06 March 2015) are taken into consideration in developing this SAP.

2 Trial Objective

The primary objective of this trial is to evaluate and describe the long-term safety of Tolvaptan.

3 Trial Design

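### Section 3.7.5 ends participation at permanent discontinuation while 3.8.3 and 3.12 prefer off-drug visits, so offset and de-challenge data may be incomplete for an open nonserious liver abnormality

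*Protocol*

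**What the plan says.** **Exit rule.** Protocol 3.7.5: "A subject who permanently discontinues IMP treatment ends trial participation and the early termination visit should be completed".

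**Stay-in preference.** Protocol 3.8.3: "It is preferred that subjects who permanently discontinue IMP will have the option to continue participation off IMP with regular scheduled visits"; a less frequent schedule is also allowed, and the early termination visit is the fallback for those unable or unwilling to continue. Protocol 3.12 prefers that subjects who stop tolvaptan, or whom the investigator withdraws for reasons other than noncompliance or loss to follow-up, "will continue with regularly scheduled visits completing all procedures as provided in the protocol". SAP 6.4 repeats 3.12. The UK version has the same three protocol statements.

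**After exit.** ALT is scheduled at the early termination visit (3.7.1.5) and the 7-day (+7) follow-up visit (3.7.1.6). Section 5.5 limits AE follow-up to 7 days after the last dose. For nonserious events at the last scheduled contact, 5.5.1 says: "All nonserious events that are ongoing at this time will be recorded as ongoing on the eCRF". Serious events differ: "The investigator will follow SAEs until the events are resolved, or the subject is lost to follow-up" (5.5.2).

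**Liver provisions.** Section 3.7.2.4.1 asks for at least weekly testing in the first month of abnormal values, then tapering. Section 3.7.2.4.2 makes a liver eCRF mandatory on stated triggers and asks that it be kept up to date. Section 5 expects medical follow-up of events of special interest and names liver abnormalities.

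**Variables.** Protocol 3.5.1 and SAP 8 list time of offset (below 3x, 2x or 1x ULN) and response to de-challenge.

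**The concern.** A site holds two current instructions for the same subject: close out at the early termination visit, or offer visits off drug. The choice can decide whether recovery from a liver abnormality is recorded.

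It bears on the signal that Protocol 1.3 treats as the most notable safety issue of chronic use. Under 3.7.2.4.1, subjects above 8x ULN, or above 5x ULN for more than 2 weeks, would not usually restart. The plan thus steers some of its most informative liver cases toward the point at which 3.7.5 ends participation. Those thresholds do not by themselves meet the SAE definition in 5.1, except through medical judgment, so following SAEs to resolution does not reliably cover them.

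At stake are the completeness of the reversibility description and the follow-up of the subject.

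**Working it through.** The plan states no figure on this point, so the check compares texts and then counts tests.

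**1. Can the rules be read together?** Section 3.7.5 ends participation for anyone who permanently discontinues. Section 3.8.3 says the same person should preferably have the option to stay. The first removes what the second offers, so no reading satisfies both. The 06 March 2015 amendment (Amendment 2 globally, Amendment 3 in the UK) was meant in part "to provide clarification on trial discontinuation". Its change table shows that the off-drug option was then taken out of 3.7.5. The current 3.8.3 and 3.12 still carry the preference. SAP Section 1 says that the original protocol and Amendments 1 and 2 "are taken into consideration in developing this SAP", yet SAP 6.4 carries it too.

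**2. How long is the fixed off-drug window?** Taking the follow-up visit as 7 to 14 days after the last dose, and the only reversal time given (about 4 months, Protocol 2.1) as 120 days:

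- 7 / 120 = 5.8%
- 14 / 120 = 11.7%

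The 4 months follow the sentence on subjects who reached Hy's laboratory criteria. Those cases may have been SAEs, so this is not a recovery time for nonserious cases.

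**3. How many retests fall after the last scheduled ALT?** Assumed schedule from 3.7.2.4.1: weekly to day 28, then monthly, that is days 7, 14, 21, 28, 58, 88 and 118 from detection. The retest within 72 hours falls before exit closes and is not counted. Abnormal durations of 30 and 60 days are assumptions.

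Retests after exit = retests due while abnormal − retests due up to the last scheduled ALT.

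| Values abnormal to | Retests due | Last ALT day 7 | Last ALT day 14 | Drug interrupted first, exit decided day 28 | Exit decided after values are normal |
|---|---|---|---|---|---|
| Day 30 | 4 | 4 − 1 = 3 | 4 − 2 = 2 | 4 − 4 = 0 | 0 |
| Day 60 | 5 | 5 − 1 = 4 | 5 − 2 = 3 | 5 − 4 = 1 | 0 |
| Day 120 | 7 | 7 − 1 = 6 | 7 − 2 = 5 | 7 − 4 = 3 | 0 |

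The day-7 and day-14 columns put detection, last dose and permanent discontinuation all on day 0, which is the extreme case. In the interruption column the closing ALT falls between day 28 and day 42, and no retest is due between those days, so the count is the same throughout.

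Full ranges: 0 to 3, 0 to 4 and 0 to 6. These are tests with no stated end point or capture rule after exit, not tests known to be lost.

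**The case against.** A reader might infer that a nonserious liver abnormality open at exit has no offset or de-challenge data at all. The documents do not support that:

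- ALT is scheduled at both the early termination and 7-day visits, and 3.7.6 refers to a post-treatment follow-up page that covers withdrawing subjects.
- The liver eCRF is mandatory for any subject who discontinues for a liver-related AE, serious or not, and for ALT or AST at or above 3x ULN after normal screening levels (3.7.2.4.2). Such abnormalities are also reportable within 24 hours (5.1, 5.3).
- The retest rule in 3.7.2.4.1 is not limited to subjects on drug or in the trial.

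Other fair points: temporary interruption often comes before a permanent decision, so off-drug values may already be recorded while the subject is still in the trial. The amendment history suggests that 3.7.5 is the intended rule and the preference is left over. SAP 6.4 gives sites no instruction. Text after the 7-day ALT and after the liver eCRF triggers is blacked out, and most of the SAP laboratory section is not in the available copy, so a censoring rule for offset may exist.

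All of this stands, and it narrows the point to incomplete data. It does not remove the conflict, because sites work from current text. Nor does any visible provision say how long retesting and eCRF updating run once participation has ended; apart from the mandatory form, they rest on what should happen or is expected.

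**Conclusion.** The conflict is real and in current text in both protocol versions, and SAP 6.4 repeats the side that 3.7.5 contradicts. If 3.7.5 is followed, time of offset and response to de-challenge may be incomplete for a nonserious liver abnormality open at permanent discontinuation. Subjects only temporarily interrupted stay in the trial, and SAEs are followed to resolution, so neither group is affected.

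The size rests on the assumed retest schedule and abnormal durations above, and every range starts at 0. A reader might go further and infer that the reversibility summaries are biased in a known direction. The text gives no basis for a size or direction, nor for how many subjects would be open at exit. The point is worth fixing because it corrects contradictory rules about the main safety signal. With no formal endpoints and only descriptive summaries planned, no test is affected.

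**What to change.** In both protocol versions:

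1. Reconcile 3.7.5 with 3.8.3 and 3.12, stating whether a subject who permanently discontinues stays for off-drug visits, and align SAP 6.4.
2. Whichever is chosen, state in 5.5 and 5.5.1 that the 7-day limit does not close a liver abnormality that meets the liver eCRF criteria and is open at the last contact. Step 1 alone is not enough, because 3.8.3 also requires withdrawal when the investigator judges that an AE or laboratory abnormality warrants it.
3. In 3.7.2.4.2, require the 3.7.2.4.1 retests to be entered in the liver eCRF until values return to the 3.5.1 offset levels, stabilize, or the subject is lost.
4. In the SAP, report unresolved cases as censored at the last test, unless text not visible already does so.

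**Cost.** A few sentences, plus eCRF entry of tests already called for: at most 6 further entries per subject over 120 days on the schedule above. Some liver eCRF files would stay open for up to a few months. That number is expected to be small but cannot be determined. The rates in Protocol 2.1 for ALT above 3x ULN over 3 years (1% placebo, 4.4% tolvaptan) applied to 2,500 subjects give 2,500 × 0.01 = 25 and 2,500 × 0.044 = 110. These do not bound the count: bilirubin, AST and liver-related discontinuations also trigger the form, and the share open at exit is not given. If step 1 favors 3.8.3, continued off-drug visits are an added cost not estimated here.

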3.7.6 End of Trial

The End of Trial date is defined as the last date of contact or the date of final contact attempt from the post-treatment Follow-up CRF page for the last subject completing or withdrawing from the trial.

3.7.7 Independent Data Monitoring Committee

For this trial, an Independent Data Monitoring Committee (IDMC), also known as a Data Safety and Monitoring Committee, will be established. The role of the IDMC shall be delineated in a separate IDMC Charter document, but in general this group will meet on a regular basis to ensure the safe and ethical treatment of trial subjects, ensure the scientific integrity of the trial, and to ensure the trial is conducted within the bounds of ethical medical practice. Adjudication results as determined by the HAC will be reported to the IDMC on a quarterly basis or more frequently as necessary. This IDMC may make recommendations to the sponsor and trial steering committee to amend or terminate the trial based on grounds of safety, futility, or greater than expected efficacy as defined by the accepted statistical practices and procedures detailed in their Charter.

Protocol 156-13-211

3.8 Stopping Rules, Withdrawal Criteria, and Procedures

3.8.1 Entire Trial

If the sponsor terminates or suspends the trial for safety or unanticipated other reasons, prompt notification will be given to investigators, IRBs/IECs, and regulatory authorities in accordance with regulatory requirements.

3.8.2 Individual Site

The investigator will notify the sponsor promptly if the trial is terminated by the investigator or the IRB/IEC at the site. If the investigator, IRB/IEC or sponsor decides to terminate or suspend the trial's conduct at a particular center for safety, non-enrollment of subjects, non-compliance with the protocol, or unanticipated other reasons, the above and other parties, as required by the applicable regulatory requirements, will be promptly notified.

3.8.3 Individual Subject

If a subject discontinues the trial prematurely, the reason must be fully evaluated and recorded appropriately in source documents and the CRF. If the subject is being withdrawn because of an AE, that AE should be indicated as the reason for withdrawal.

All subjects have the right to withdraw at any time during treatment without prejudice. The investigator can discontinue a subject's participation in the trial at any time if medically necessary. It is preferred that subjects who permanently discontinue IMP will have the option to continue participation off IMP with regular scheduled visits or with a modified (ie, less frequent) schedule. If subjects are unable or unwilling to complete the visits and procedures off IMP, the early termination/EoTx visit should be completed. The investigator may continue to contact those who discontinue IMP through to the final completion date of the trial or thereafter if needed to determine outcomes ie, vital status.

In addition, subjects meeting the following criteria must be withdrawn from the trial:

- a) Occurrence of any AE, intercurrent illness, or abnormality in a laboratory assessment which, in the opinion of the investigator, warrants the subject's permanent withdrawal from the trial;
- b) Subject noncompliance, defined as refusal or inability to adhere to the trial schedule or procedures (see [Section 3.12](#));
- c) At the request of the subject, investigator, sponsor, or regulatory authority;
- d) Subject is lost to follow-up.

Protocol 156-13-211

The investigator will notify the sponsor promptly when a subject is withdrawn.

3.9 Screen Failures

A screen failure subject is one from whom informed consent is obtained and is documented in writing (ie, subject signs an ICF), but who is not started on treatment.

3.10 Definition of Completed Subjects

For purposes of this trial, subjects who complete the EoTx visit will be defined as trial completers.

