After consenting, subjects will be assigned a new screening number. Subjects who are found to be eligible will retain the same subject number they had been assigned in their previous trial. For purposes of ensuring subject safety, tolvaptan exposure of at least 18 months is required for all subjects. While Trial 156-13-210 remains blinded, subjects enrolling from any prior trial besides Trial 156-08-271 are scheduled to have monthly hepatic monitoring for the first 18 months of this trial. After that, following the approval of the medical monitor, hepatic monitoring will take place every 3 months. Subjects enrolling from Trial 156-08-271 will have hepatic monitoring every 3 months. All Trial 156-13-210 subjects who are eligible for this trial will initially be scheduled to have trial visits and hepatic monitoring monthly for the first 18 months, then every 3 months thereafter, because their tolvaptan exposure cannot be determined since Trial 156-13-210 is a double blind trial. Once unblinding occurs, it can be determined which subjects received tolvaptan in Trial 156-13-210. These subjects may have their trial visits/hepatic transaminase monitoring changed to every 3 months sooner as their previous tolvaptan exposure in Trial 156-13-210 can count towards the 18-month threshold. Subjects from prior tolvaptan trials other than Trial 156-08-271 will have monthly trial visits/ALT level assessments for the first 18 months. After that, the trial visits/ALT monitoring will be conducted every 3 months after the change in frequency is confirmed with the medical monitor.

Enrollment in this trial will be closed when the last eligible subject from Trial 156-13-210 enrolls in this trial.

The duration of this trial is planned to continue

- Until the last subject from Trial 156-13-210 completes 18 months of tolvaptan treatment in this trial
- Subjects enrolling from other trials will conclude their participation once tolvaptan becomes available through routine prescription or through a CCI Trial 156-13-210 subjects may opt to conclude their participation in this trial if tolvaptan becomes available before they complete 18 months of treatment in this trial

Protocol 156-13-211

[figure not shown]

Figure 3.1-1 Trial Design Schematic

Protocol 156-13-211

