3.7.1.5 Early Termination/End of Treatment (+ 7 days)

At the early termination/end of treatment (EoTx) visit the following will be assessed:

1. Review dietary recommendations and compliance.

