3.4 Trial Visit Window

Due to the extended duration of the study, the individual patient data will be summarized by period.

For assessments recorded at clinic visits, except for the hepatic monitoring for the subjects from Trial 156-08-271, data will be derived by mapping the study day of the assessment into corresponding time windows as specified in [Table 3.4.1](#). Study day is calculated as: date of assessment - date of enrollment (ie, screening or baseline date) + 1. If there are multiple observations within the same study time window, only the last observation within that study week will be used for the summary tables. The time window mapping rules are applicable to all post first dose safety and efficacy assessments (unless otherwise stated) that are assessed at the scheduled or unscheduled visits (excluding early termination visits/end of treatment visits).

Table 3.4.1 Mapping of clinic visit assessments to study month (except for hepatic monitoring for Subjects from Trial 156-08-271)

Study Month	Study Day Interval
Monthly Visit	
Month 1	2 – 46
Month 2	47 – 76
Month 3	77 – 107
Month 4	108 – 137
Month 5	138 – 168
Month 6	169 – 198
Month 7	199 – 229
Month 8	230 – 259
Month 9	260 – 290
Month 10	291 – 320
Month 11	321 – 351
Month 11	352 – 381
Month 13	382 – 412
Month 14	413 – 442

Protocol 156-13-211

Month 15	443 – 473
Month 16	474 – 503
Month 17	504 – 534
Month 18	535 – 595
Every 3 Months	
Month 21	596 – 686
Month 24	687 – 778
Month 27	779 – 869
Month 30	870 – 961
Month 33	962 – 1052
Month 36	1053 – 1144
Month 39	1145 – 1235
Month 42	1236 – 1327
Month 45	1328 – 1418
Month 48	1419 – 1510
Month 51	1511 – 1601
...	...

Note: Early Termination/End of Treatment (\pm 7 days)

Once Trial 156-13-210 unblinding occurs, it can be determined which subjects received tolvaptan in Trial 156-13-210. These subjects may have their trial visits/hepatic transaminase monitoring changed to every 3 months sooner as their previous tolvaptan exposure in Trial 156-13-210 can count towards the 18-month threshold.

For assessments for hepatic monitoring recorded at clinic visits, for the subjects from Trial 156-08-271, data will be derived by mapping the study day of the assessment into corresponding time windows as specified in [Table 3.4.2](#).

Study Month	Study Day Interval
Every 3 Months (\pm 45 days)	
Month 3	2 – 137
Month 6	138 – 229
Month 9	230 – 320
Month 12	321 – 412
Month 15	413 – 503
Month 18	504 – 595
Month 21	596 – 686
Month 24	687 – 778
Month 27	779 – 869

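### Protocol 3.10 can count subjects who stop early as completers if they attend the combined early termination/EoTx visit, and the status of availability exits is not stated

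*Protocol*

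**What the plan says.** Protocol 3.10 gives the only definition of completion in either document: "subjects who complete the EoTx visit will be defined as trial completers". It sets no minimum time in the trial and does not require the subject to be on drug or at a planned end. The UK protocol's 3.10 is identical.

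The visit itself is described in Protocol 3.7.1.5: "At the early termination/end of treatment (EoTx) visit the following will be assessed". It has one procedure list, and the schedule of assessments (Table 3.7-1) has one column for both kinds of exit.

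Two sections send early stoppers to it. Section 3.7.5: "A subject who permanently discontinues IMP treatment ends trial participation and the early termination visit should be completed". Section 3.8.3, for those who stop drug and will not stay in follow-up: "If subjects are unable or unwilling to complete the visits and procedures off IMP, the early termination/EoTx visit should be completed".

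Section 3.8.3 also requires the cause to be kept: "If a subject discontinues the trial prematurely, the reason must be fully evaluated and recorded appropriately in source documents and the CRF".

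On availability, Protocol 3.1 says: "Subjects enrolling from other trials will conclude their participation once tolvaptan becomes available through routine prescription" (or through the other access routes listed there). For the other group: "Trial 156-13-210 subjects may opt to conclude their participation in this trial if tolvaptan becomes available before they complete 18 months of treatment". The UK protocol makes this exit optional for subjects from every parent trial.

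SAP 6.1 tabulates disposition and reasons for discontinuation by parent study and parent-study treatment. It does not define completion and lists no reason categories. SAP 5.2 relies on that table to show the pattern of drop-out.

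**The concern.** A disposition table has one main job: to separate subjects who finished from those who did not. Here the written rule for finishing is attendance at a visit that subjects who did not finish are also told to attend. If a programmer applies 3.10 as it stands, some adverse event stops and withdrawals can land in the completer row, and they may then not appear among the discontinuations with their reasons.

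The second gap is the exit because tolvaptan becomes available elsewhere. It is neither a safety stop nor drop-out in the usual sense, and the rule differs by parent trial. With no stated status, it could be put in either row. SAP 6.1 reports by parent study, so the choice bears on exactly the comparison a reader of that table would make.

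At stake is whether the completed and discontinued counts, and the drop-out description that SAP 5.2 draws from them, mean what a reader will take them to mean.

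**Working it through.** No arithmetic applies. The plan gives no completion, drop-out or attendance figure to reproduce; the sample size text gives only an expected enrolment of about 2,500. The check is to read the sections together.

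**Step 1: is the EoTx visit distinct from early termination?** Section 3.7.1.5 attaches the abbreviation EoTx to the combined visit, and the schedule gives that visit one column. Section 3.8.3 also uses the combined name. The abbreviation list expands it as end of treatment only, and 3.7.5 speaks of the early termination visit. The weight of the text is for one shared visit, with some looseness. SAP 3.4 names the two side by side ("excluding early termination visits/end of treatment visits"), but only to leave them out of window mapping, so it settles nothing.

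**Step 2: apply 3.10 literally to each kind of exit.**

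| Exit | Sent to the visit by | Meets 3.10 if the visit is attended? | Status implied elsewhere |
|---|---|---|---|
| On drug at trial closure | 3.7.1.5 | Yes | Completed |
| Permanent stop for an AE | 3.7.5, 3.8.3 | Yes | Premature discontinuation (3.8.3, 3.11) |
| Withdrawal by the subject | 3.7.5, 3.8.3 | Yes | Premature discontinuation (3.8.3, 3.11) |
| Availability exit, not from Trial 210 | Not stated; end of treatment in this trial | Yes | Planned end (3.1); status not stated |
| Availability exit before month 18, from Trial 210 | Not stated; end of treatment in this trial | Yes | Optional (3.1); status not stated |
| Lost to follow-up, or leaves without the visit | Not attended | No | Discontinued (3.11) |

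**Step 3: does this clash with other text?** Yes, for rows two and three. Section 3.8.3 treats such subjects as leaving the trial early, 3.11 gives withdrawn consent and AE as examples of reasons for discontinuation, and SAP 5.2 sets drop-out against completion. The literal rule can place the same subjects on the other side of that line.

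**Step 4: does the SAP repair it?** No. SAP 6.1 has no definition, and SAP 13 records no change to the planned analyses.

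**Step 5: what depends on the label?** SAP 5.1 defines an Enrolled and a Safety Population and no completer population. SAP 8 analyses all enrolled subjects who took at least one dose, without inference. Only the disposition table, and the drop-out description built on it, can be affected.

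**The case against.** The best defence is that nobody would read 3.10 this way. The abbreviation means end of treatment, 3.7.5 uses a different visit name, and 3.8.3, 3.11 and SAP 5.2 plainly regard adverse event stops and withdrawals as discontinuations. The SAP never uses the word completer, reasons must be recorded, SAP 6.1 tabulates them, and discontinuations due to TEAEs have their own summary.

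Much of this stands. It shows that the sponsor probably meant the narrower reading and that the data to apply it should exist. It does not remove the problem: the only written rule says otherwise, and the sections that contradict it do not replace it.

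Three stronger readings are tempting, and the documents do not support them:

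- A reader might infer that every adverse event stop and withdrawal will be reported as a completer. Only those who attend the visit could be, and only if 3.10 is applied as worded.
- A reader might infer that SAP 6.1 overlooks availability in particular. It lists no reason categories at all, and the CRF, which is not among the documents, may well have one.
- A reader might infer that the months-completed table in SAP 6.1 is wrong because it mixes exit types. It is a correct count of time in the trial, and the SAP makes no retention claim from it.

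It is also fair that, for subjects not from Trial 210, leaving on availability is a planned end under Protocol 3.1, so calling them completers is defensible. The ambiguity is sharpest for Trial 210 subjects who opt out before month 18, and for UK subjects, for whom the exit is optional whatever the parent trial.

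**Conclusion.** The point holds in limited form. As written, Protocol 3.10 can label as completers subjects whom 3.8.3, 3.11 and SAP 5.2 treat as having discontinued, and neither document states the status of an availability exit. The definition should be corrected before the disposition table is produced.

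The consequence is limited to the completed and discontinued counts and the drop-out description. A reader might infer that the safety results are compromised; they are not, because those analyses include all dosed subjects and TEAE discontinuations are summarised separately.

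The size cannot be known. It depends on how many subjects stop permanently, how many of those attend the visit, how many leave on availability, and whether the table is programmed from 3.10 or from recorded reasons. The documents give none of these. The conclusion assumes only that 3.10 would be applied as worded.

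**What to change.** In SAP 6.1, and in Protocol 3.10 if it is amended, give each subject one status:

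- **Completed:** on tolvaptan at trial closure, or at the subject's protocol-planned end of participation.
- **Concluded because tolvaptan became available:** its own row by parent study, counted as neither drop-out nor AE discontinuation. Availability exits go here even where they are the planned end, so that no subject is counted twice. A reader who regards the planned exits of subjects not from Trial 210 as completion can add the rows.
- **Discontinued:** any other permanent stop, with its reason.

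Add one sentence saying that attending the early termination/EoTx visit does not by itself mean completion.

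The cost is one definition and one table row, with no new visits or assessments. Reasons are already required by 3.7.5 and 3.8.3; if the CRF has no code for availability, the row would have to be derived from the recorded reason text. If only the SAP is changed, it will differ from Protocol 3.10, and SAP 13 should say so.
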